9.1.1 Dose Escalation and Expansion

A classical “3+3” study design will be used to estimate the MTD for CAR-specific T cells treatment among patients with newly-diagnosed WHO grade IV malignant glioma. As shown below in [Table 3](#), 4 dose levels will be considered based on transduced cells/kg: #1: 4.5 x 10⁶/kg, #2: 1.5 x 10⁷/kg, #3: 4.5 x 10⁷/kg, and #4: 1.5 x 10⁸/kg.

Table 3. Dose Escalation and Expansion

Dose Escalation and Expansion			
Cohort	Dose of CAR-specific T cells	# of Subjects	Schema
1	4.5 x 10 ⁶ /kg	3-6	Dose escalation: “Standard 3+3”
2	1.5 x 10 ⁷ /kg	3-6	
3	4.5 x 10 ⁷ /kg	3-6	
4	1.5 x 10 ⁸ /kg *	3-6	
* If the patient’s targeted dose is 1.5 x 10 ⁸ /kg (dose level #4), the calculated dose will be capped at 1.0 x 10 ¹⁰ total cells.			

Starting with the lowest dose level, cohorts of 3-6 subjects will be accrued at each dose level according to the following dose escalation rules:

Table 4. Dose Escalation Rules

Number of patients with DLT observed during the first 4 weeks after CAR treatment	Escalation Decision Rule
0 out of 3	Enter 3 patients at the next dose level
1 out of 3	Enter 3 more patients at this dose level. 
 If 0 of these 3 patients experience DLT, proceed to the next dose level If 1 or more of this group suffer DLT, then dose escalation is stopped. Three (3) additional patients will be entered at the next lowest dose level if only 3 patients were treated previously at that dose.

≥ 2	Dose escalation will be stopped. Three (3) additional patients will be entered at the next lowest dose level if only 3 patients were treated previously at that dose.
DLT = dose limiting toxicity; MTD = maximum tolerated dose	

If a patient terminates the infusion of EGFRvIII CAR T cells prematurely or is lost to follow-up during the first 4 weeks after CAR treatment without experiencing a DLT, then the patient will not be evaluable for the determination of the MTD and will be replaced. The MTD is the highest dose level at which ≤ 1 of 6 patients experiences DLT during the 4 week observation period after CAR treatment. The last patient in a given cohort, receiving that dose level, should be observed for DLTs for at least 4 weeks prior to moving on to the next cohort/higher dose. Section 9.1.2 provides information about what constitutes a DLT.

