An expanded cohort of a total of 12 patients will be enrolled at the MTD of EGFRvIII CAR T cells in order to obtain a more precise estimate of the probability of unacceptable toxicity. This cohort will also have the cells radiolabeled with ^{111}In to track their distribution. Briefly, CARs will be counted and re-suspended in PBS. $4\text{-}6 \times 10^8$ cells will be labeled with 500 micro Ci of ^{111}In . The cells will be washed and mixed with cold CARs to achieve the desired cell dose with a total of 500 μCi of ^{111}In . The labeled CARs will be infused into the patient through an intravenous catheter within the Ambulatory Bone Marrow Transplant (BMT) Unit. Distribution of ^{111}In -labeled EGFRvIII CARs will be evaluated at 1, 2, and 3 days post-infusion using whole body planar imaging followed by SPECT/CT, when indicated.

In the rare event that a sufficient amount of CAR-specific T cells cannot be generated for a patient's intended dose within the dose-escalation portion of this study, the patient will be treated at a lower pre-defined dose level using available CAR-specific T cells. If this patient experiences a DLT, data will be carefully reviewed to determine its impact upon dose escalation and future patient treatment. If this situation occurs with the expanded cohort, all available cells will be administered.

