9.5 Early Study Termination

This study can be terminated at any time for any reason by the PI-sponsor. If this occurs, all subjects on study will be notified as soon as possible. Additional procedures and/or follow up should occur in accordance with Section 12.7, which describes procedures and processes for prematurely withdrawn patients.

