13.1.1 Reporting of AEs

A summary of all adverse events (not just those considered related to EGFRvIII CARs) that occur following treatment with EGFRvIII CARs will be kept which will categorize the event by organ system, relationship to treatment, its grade of severity, and resolution. The PI will periodically review the collective adverse events with the intention of identifying any trends or patterns in toxicity. If any such trends are identified, depending on their severity and frequency, a protocol amendment will be considered.

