13.4 Safety Oversight Committee (SOCom)

The Duke Cancer Institute SOCom is responsible for annual data and safety monitoring of DUHS sponsor-investigator phase I and II, therapeutic interventional studies that do not have an independent DSMB. The primary focus of the SOCom is review of safety data, toxicities and new information that may affect subject safety or efficacy. Annual safety reviews includes but may not be limited to review of safety data, enrollment status, stopping rules if applicable, accrual, toxicities, reference literature, and interim analyses as provided by the sponsor-investigator. The SOCom in concert with the DCI Monitoring Team (see [Monitoring](#) section for Monitoring Team description) oversees the conduct of DUHS cancer-related, sponsor-investigator therapeutic intervention and prevention intervention studies that do not have an external monitoring plan, ensuring subject safety and that the protocol is conducted, recorded and reported in accordance with the protocol, SOPs, GCP, and applicable regulatory requirements.

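### No DLT count obliges a pause, a review or a re-evaluation of the MTD during the 12-patient expansion, and the plan does not say whether expansion data can overturn the MTD

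*Combined protocol and SAP*

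**What the plan says.** **Escalation.** In section 9.1.1, "cohorts of 3-6 subjects will be accrued at each dose level according to the following dose escalation rules". Under Table 4, 2 DLTs among up to 6 patients stop escalation. The last patient in a cohort "should be observed for DLTs for at least 4 weeks prior to moving on to the next cohort/higher dose". The outcome is fixed by a six-patient criterion: "The MTD is the highest dose level at which ≤ 1 of 6 patients experiences DLT during the 4 week observation period after CAR treatment". Section 15.4 repeats it.

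**Expansion.** The same section then says "An expanded cohort of a total of 12 patients will be enrolled at the MTD of EGFRvIII CAR T cells". Two reasons are given: a sharper toxicity estimate, and cell tracking. No decision is attached to that estimate. Section 15.5 tabulates DLT proportions by dose level, and section 15.7 anticipates 18 patients at the MTD (6 plus 12).

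**Oversight.**
- Section 13.4: "The Duke Cancer Institute SOCom is responsible for annual data and safety monitoring". Stopping rules are reviewed where they apply, but none is given for the expansion.
- Section 13.1.1: "The PI will periodically review the collective adverse events with the intention of identifying any trends or patterns in toxicity". An amendment may then be considered.
- Section 9.5: "This study can be terminated at any time for any reason by the PI-sponsor".
- Section 14.1: routine monitoring follows the third subject and is then annual, on 1 to 3 subjects. Extra monitoring may follow an unexpected frequency of toxicity.
- Sections 9.1.2 and 13.3.1: listed DLTs go to the FDA, and SAEs are reported immediately, including to the FDA and IRB.

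**Analysis set.** Section 15.1 builds the MTD Analysis Set from everyone who received any CAR treatment, less patients without DLT who are not evaluable. Expansion patients are not excluded.

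**The concern.** Six patients are a weak screen for toxicity, and the expansion treats twice as many again at the chosen level. An over-toxic MTD would therefore show itself in the expansion. During escalation, 2 DLTs in 6 rule a level out. During expansion at that same level, 6 in 12 would oblige no one to pause or reconsider.

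Two things are at stake. One is the protection of expansion patients, which rests on judgement with no stated point at which it must be exercised. The other is the primary result: if the data gathered to check the MTD contradict it, the plan does not say which prevails.

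**Working it through.** **The plan's own figure.** Table 7 is the only quantitative support for the expansion. It gives 95% half widths of 0.025, 0.032, 0.039, 0.044 and 0.047 at DLT rates of 0.05, 0.10, 0.15, 0.20 and 0.25. The usual formula, 1.96 × √(p(1−p)/18), gives 0.101, 0.139, 0.165, 0.185 and 0.200, so the printed values are about four times too small. That is a separate matter. Here it matters only that Table 7 concerns precision and contains no decision rule.

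**Inputs.** From the documents: 6 patients and at most 1 DLT to qualify as MTD; 12 expansion patients; 18 in total; a 4-week DLT window. Assumed: true DLT rates p from 10% to 50%, since the documents give none (Table 7 spans 5% to 25%). Below, 17% means 1/6 and 33% means 1/3.

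**Step 1: how well six patients screen.** P(at most 1 DLT in 6) = (1−p)⁶ + 6p(1−p)⁵. At p = 1/3 this is 0.088 + 0.263 = 0.351.

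**Step 2: what the expansion would show.** Expected DLTs = 12p. P(at least 4 in 12) is the binomial tail.

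| True rate | P(≤1 in 6) | Mean DLTs in 12 | P(≥4 in 12) |
|---|---|---|---|
| 25% | 0.53 | 3.0 | 0.35 |
| 33% | 0.35 | 4.0 | 0.61 |
| 40% | 0.23 | 4.8 | 0.78 |
| 50% | 0.11 | 6.0 | 0.93 |

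With 1 DLT in 6, the exact 95% interval for the DLT rate runs from 0.4% to 64%.

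**Step 3: what a count rule could do.** As an illustration only, suppose enrolment pauses when cumulative DLTs at the MTD reach one third of treated patients, the 2-in-6 proportion at which Table 4 stops escalation. The boundary is 3 of 7–9, 4 of 10–12, 5 of 13–15 or 6 of 16–18.

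Let x₀ be the DLTs among the first 6. Let f_i(k) be the probability that enrolment is still open after i expansion patients with k DLTs among them, with f_0(0) = 1. Then f_i(k) = (1−p)·f_{i−1}(k) + p·f_{i−1}(k−1) for every k with 3(k + x₀) < 6 + i; otherwise that probability counts as a pause. P(pause) = 1 − Σ f_12(k). Mean patients treated is the sum of f_i(k) over k and over i = 0 to 11.

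| True rate | P(pause), from 1/6 | Mean treated | P(pause), from 0/6 | Mean treated |
|---|---|---|---|---|
| 10% | 0.04 | 11.7 | 0.00 | 12.0 |
| 17% | 0.12 | 11.1 | 0.02 | 11.9 |
| 25% | 0.30 | 9.9 | 0.09 | 11.6 |
| 33% | 0.52 | 8.5 | 0.23 | 11.0 |
| 40% | 0.69 | 7.2 | 0.40 | 10.2 |
| 50% | 0.87 | 5.5 | 0.66 | 8.7 |

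P(pause) includes a trigger at the twelfth expansion patient, which prompts review but spares no one. The means assume that each outcome is known before the next infusion. If three more patients are treated before each outcome is known, the means from 1/6 become 9.9, 9.1 and 8.0 at 33%, 40% and 50%.

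**The case against.** A reader might infer that all 12 patients would be treated whatever happened, with only a yearly look. The documents do not support that. The PI-sponsor can end the study at any time, a toxicity trend can lead to an amendment, SAEs and listed DLTs are reported promptly, and for-cause monitoring is available. These are real safeguards. None has a threshold, however, and none requires a pause.

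A reader might also infer that the MTD cannot be corrected by expansion data. That is not established either. The MTD Analysis Set does not exclude these patients, and neither the evaluability definition in section 9.4 nor the replacement rule in section 12.7.3 is confined to escalation. The definition of at most 1 in 6 simply does not say how 18 patients are to be read. This is an ambiguity, not a prohibition.

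Three quantitative objections stand:
- Passing at most 1 in 6 is necessary but not sufficient for being declared the MTD. Escalation must also reach the level, and the next level must fail or not exist. The probabilities in step 1 are therefore upper bounds.
- The illustrative rule does much less when the expansion starts from 0 DLTs in 6.
- Its saving in patients exposed shrinks when outcomes lag behind enrolment.

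Finally, a sponsor may reasonably prefer another boundary. Nothing in the documents makes one third the right one.

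**Conclusion.** The gap is real and should be closed, though it falls short of a fatal flaw. During the expansion no DLT count obliges a pause, an unscheduled review or a re-evaluation of the MTD. Any halt is discretionary, so its operating characteristics cannot be stated. Separately, the plan does not say whether the 18-patient data can overturn an MTD defined on 6.

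The size depends on an assumed true DLT rate. Over 25% to 50%, a level passes the six-patient screen with probability 0.53 down to 0.11, and the expansion would average 3.0 to 6.0 DLTs. These figures assume independent patients with a common DLT rate. The absence of a count-based rule rests on the text alone and needs no assumption.

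**What to change.** - **Sections 9.1.1 and 13.4:** state that DLTs at the MTD are tallied cumulatively through the expansion, and that reaching a prespecified count pauses new enrolment for prompt SOCom review.
- **Section 15.4:** state that the MTD is confirmed or withdrawn on the combined escalation and expansion data, and by what criterion.
- **Operating characteristics:** the sponsor chooses the boundary and reports its pause probability over a range of true rates, from both 0 and 1 DLT in the first 6. It also states how patients still inside the 4-week window are handled.

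The change needs no extra patients. It costs protocol wording, an unscheduled review if triggered, and some unnecessary pauses: under the illustrative rule from 1 in 6, 4% at a true rate of 10%, 12% at 17% and 30% at 25%. Waiting out the DLT window after every patient would preserve the full saving in exposure but could add up to 12 × 4 = 48 weeks. Without staggering, the saving is smaller. The sponsor should state which of these it accepts.

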9.1.2 Definition of Dose-Limiting Toxicity (DLT)

The DLT observation period is the 4 weeks after EGFRvIII CAR T cell infusion. Toxicities will be graded according to the NCI CTCAE version 4 criteria. A DLT will be defined as any Grade IV event of any duration that is at least (possibly, probably, or definitely) attributable to EGFRvIII CARs, or any Grade III toxicity that is at least (possibly, probably, or definitely) attributable to EGFRvIII CARs that is not reversible within 4 weeks. DLT definition includes and will be reported to FDA all of the following:

- a. Any treatment-emergent CTCAE Grade 4 or 5 CRS.
- b. Any treatment-emergent CTCAE Grade 3 CRS that do not resolve to \leq Grade 2 within 7 days.
- c. Any treatment-emergent autoimmune toxicity \geq Grade 3.
- d. CTCAE grade 3-5 allergic reactions related to the study cell infusion.
- e. CTCAE grades 3 and greater organ toxicity (cardiac, dermatologic, gastrointestinal, hepatic, pulmonary, renal/genitourinary, or neurologic) not pre-existing or due to the underlying malignancy and occurring within 30 days of study product infusion.

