9.4 Definition of Evaluable Subjects, On Study, and End of Study

While all patients who received any EGFRvIII CAR T cells will be included in safety summaries for the purposes of monitoring and reporting of adverse events to appropriate agencies, patients evaluable for determination of the MTD will include:

- Patients who receive the entire CARs infusion (i.e. the infusion is not stopped prematurely), and 2) have 4 weeks of follow-up for adverse events after the infusion
- Patients who receive the entire CARS infusion (i.e. the infusion is not stopped prematurely) and terminated follow-up prematurely during the 4 week follow-up period after having experienced a DLT.
- Patients who terminate infusion before completion due to a DLT

For the efficacy analyses, evaluable patients will include two groups of patients: all patients, and the subgroup of patients who receive EGFRvIII CAR. Once a patient's eligibility is confirmed after completion of XRT/TMZ, that subject will be considered "on study". The rationale for taking a patient off study will be documented. Please see Section 12.7 for information on patient withdrawals.

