13.1 Adverse Events

An AE is any untoward medical occurrence in a subject receiving EGFRvIII CARs and which does not necessarily have a causal relationship with this treatment. For this protocol, the definition of AE also includes worsening of any pre-existing medical condition. An AE can therefore be any unfavorable and unintended or worsening sign (including an abnormal laboratory finding), symptom, or disease temporally associated with the use of EGFRvIII CAR T cells, whether or not related to use of the EGFRvIII CAR T cells. All CTCAE-defined AEs, including grade 1 laboratory events, are recorded and reported as required in 21CFR312.

From the time of CAR T cell infusion through the End of Study visit (as defined in Section 12.6), as well as any Special Interest AEs related to leukapheresis (as defined in Section 13.2), all AEs must be recorded in the subject medical record and adverse events case report form. However, for reporting purposes, only AEs that occur at the time of the EGFRvIII CAR T cell infusion or following the infusion will be submitted to the appropriate agencies as indicated.

AEs will be assessed according to the CTCAE version 4.0. If CTCAE grading does not exist for an AE, the severity of the AE will be graded as mild (1), moderate (2), severe (3), life-threatening (4), or fatal (5).

Attribution of AEs will be indicated as follows:

- Definite: The AE is clearly related to the study drug
- Probably: The AE is likely related to the study drug
- Possible: The AE may be related to the study drug
- Unlikely: The AE is doubtfully related to the study drug
- Unrelated: The AE is clearly NOT related to the study drug

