15.1 Analysis Sets

EGFRvIII CAR Efficacy Analysis Set: Efficacy analyses will focus on two groups of patients: all patients, and the subgroup of patients who receive EGFRvIII CAR.

Overall EGFRvIII CAR Safety Analysis Set: For monitoring purposes and for reporting to appropriate agencies, safety analyses will include all patients who receive any EGFRvIII CAR treatment.

MTD Analysis Set: For the determination of MTD, patients without DLT who do not complete 4 weeks of follow-up after CAR infusion or do not complete the intended infusion will be excluded from the Overall EGFRvIII CAR Safety Analysis Set to create the MTD Analysis Set.

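### The general DLT rule omits Grade V, so a narrow class of treatment-related deaths is not a DLT as written

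*Combined protocol and SAP*

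**What the plan says.** Section 9.1.2 has two general limbs, both restricted to events at least possibly attributable to the CARs. The first is "A DLT will be defined as any Grade IV event of any duration". The second is "any Grade III toxicity that is at least (possibly, probably, or definitely) attributable to EGFRvIII CARs that is not reversible within 4 weeks". A list of specific inclusions follows:

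- (a) "Any treatment-emergent CTCAE Grade 4 or 5 CRS";
- (b) Grade 3 CRS that is slow to resolve;
- (c) autoimmune toxicity of Grade 3 or above;
- (d) allergic reactions of Grades 3 to 5;
- (e) toxicity of Grade 3 and above in seven named organ systems. Infection is not among them.

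Section 13.1, for events without CTCAE grading, separates "life-threatening (4), or fatal (5").

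Who counts towards the MTD is set in 9.4 and 15.1. Under 9.4, a patient with a complete infusion must either "have 4 weeks of follow-up for adverse events after the infusion" or have "terminated follow-up prematurely during the 4 week follow-up period after having experienced a DLT". A third route covers infusions stopped because of a DLT. Section 15.1 removes "patients without DLT who do not complete 4 weeks of follow-up after CAR infusion". Sections 9.1.1 and 12.7.3 replace treated patients who stop the infusion early or are lost to follow-up without a DLT.

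**The concern.** Neither general limb names Grade V, and the specific items reach Grade 5 only within their own categories. Section 9.1.3 itself describes a fatal product risk outside those categories: sepsis from contaminated cells. A patient who died that way could have no DLT on the written definition and then leave the MTD set for not completing 4 weeks. The DLT count drives escalation, the MTD (the primary endpoint) and the dose-level DLT proportions in 15.5. A treatment-related death is where a 3+3 rule should least need interpretation.

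**Working it through.** **1. Which attributable events count, read literally**

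| Category | Grade 4 | Grade 5 |
|---|---|---|
| CRS | DLT | DLT, item (a) |
| Autoimmune | DLT | DLT, item (c) |
| Allergic | DLT | DLT, item (d) |
| Seven listed organ systems | DLT | DLT, item (e) |
| Anything else, e.g. sepsis | DLT, limb 1 | Not a DLT, unless an attributable Grade IV event was recorded or an attributable Grade III toxicity was unresolved at death |

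The last exception follows from limb 2: a Grade III toxicity still present at death has not reversed.

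Reading Grade IV as Grade IV and above does not fit the text. Item (a) names both grades when both are meant, and 13.1 gives death its own grade. No other section closes the gap: 9.1.1 and 15.4 refer back to 9.1.2, and 13.3 makes death an SAE, not a DLT.

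**2. What happens to the patient**

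Take a complete infusion followed by such a death within 4 weeks. No route in 9.4 admits the patient, and 15.1 excludes them. Replacement names loss to follow-up, whereas 9.1 and 12.7.2 list death separately from loss. On the plain wording the patient is neither evaluable nor replaced.

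- Death in the first three, other two DLT-free: 0 of 2 evaluable. Counted properly it is 1 of 3, so three more patients enter.
- Death in the second three, after one true DLT in the first three, other two DLT-free: 0 of 2 in that group and 3 + 2 = 5 evaluable overall, so 1 of 5. Counted properly it is 2 of 6, so escalation stops.

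Table 4 has no row for a group of two, and the MTD rule is written for six patients. The rule stalls; it does not authorise escalation.

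**3. Weaker reading: the death is replaced as loss to follow-up**

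Let p be the DLT probability of each further patient. The documents give no value, so p is assumed to be 0.1, 0.2 or 0.3. The other two patients in the group are taken as DLT-free.

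- First three, counted (1 of 3): P(escalate) = (1−p)³ = 0.729, 0.512, 0.343.
- First three, replaced: P(escalate) = (1−p) + p(1−p)³ = 0.973, 0.902, 0.803.
- Second three, counted: P(escalate) = 0, since Table 4 stops.
- Second three, replaced: P(escalate) = 1−p = 0.90, 0.80, 0.70.

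**4. The same reading without conditioning on a death**

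At one dose level, Table 4 gives P(escalate) = (1−r)³ + 3r(1−r)⁵ for DLT rate r. Assume an ordinary DLT rate of 0.20 and an uncaptured-death rate q of 0.02, 0.05 or 0.10.

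- Deaths counted, r = 0.20 + q: 0.665, 0.600, 0.494.
- Deaths excluded and replaced, r = 0.20/(1−q): 0.700, 0.686, 0.660.

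**5. DLT rate at the MTD**

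With the 18 patients expected in 15.7 and one such death as the only event:

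- counted: 1/18 = 5.6% (exact 95% CI 0.1% to 27.3%);
- excluded: 0/17 = 0% (0% to 19.5%).

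The intervals overlap, and no decision rule depends on them.

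**The case against.** The strongest reply is that the class is close to empty. A fatal toxicity normally passes through a life-threatening phase, and limb 1 catches such an event however brief. Fatal sepsis would usually involve Grade 3 or worse cardiac, pulmonary or renal toxicity, which item (e) counts. The other fatal risks described in 9.1.3 are largely covered too: CRS, tumor lysis through renal or cardiac toxicity, cerebral edema and autoimmunity.

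Recording is thorough: "All CTCAE-defined AEs, including grade 1 laboratory events, are recorded and reported as required in 21CFR312". The product must pass sterility tests, although the pre-infusion cultures may not be conclusive and final-product cultures report only after infusion (Table 5, notes 3 and 4). A positive result prompts evaluation within 24 hours, and deaths remain in the safety set and are reported to the FDA and IRB. The reach of items (a), (c), (d) and (e) to Grade 5 shows that fatal toxicity was meant to count, and an investigator would very probably call such a death a DLT. On the plain wording the rule stalls, which is conservative.

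All of this bears on likelihood and severity, and it stands: unnoticed escalation is unlikely. It does not change the text. Evident intent argues for correcting the wording, because the rule as written needs someone to override it.

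A further objection is that strict reading is applied to the gap but not to the remedy. That fails. Once the death is a DLT, follow-up has ended within 4 weeks in a patient with a DLT. The second route in 9.4 then fits, and 15.1 excludes only patients without one.

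**Conclusion.** The concern holds, at minor severity. As written, an attributable death within 4 weeks is not a DLT when three things are all true: it lies outside items (a), (c), (d) and (e); no attributable Grade IV event was recorded; and no attributable Grade III toxicity was unresolved at death. The omission and the exclusion under 15.1 follow from the text and rest on no numerical assumption. On the plain wording the result is a cohort the escalation table does not cover. A wrong escalation requires the further step of replacing the death as loss to follow-up. The escalation probabilities illustrate that second reading only, on assumed rates. How often the event would occur cannot be estimated from the documents.

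**What to change.** In the lead sentence of 9.1.2, write *any Grade IV or V event of any duration*, keeping the attribution condition. Nothing else has to change: the second route in 9.4 then makes the patient evaluable, and 9.1.1, 12.7.3 and 15.1 replace or exclude only patients without a DLT. A sentence in 9.4 confirming that a patient who dies of a DLT is evaluable would be a harmless addition. The cost is two words, with no added data, visits or patients.

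### One DLT criterion runs for 30 days while escalation and the MTD count 4 weeks, and Grade 3 CRS with onset on days 22-28 can still be unclassified when the 4-week hold ends

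*Combined protocol and SAP*

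**What the plan says.** Section 9.1.2 opens with the general window: "The DLT observation period is the 4 weeks after EGFRvIII CAR T cell infusion". The same section then lists events that the DLT definition includes and that go to the FDA. Item (e) is Grade 3 or higher toxicity of a listed organ system, "not pre-existing or due to the underlying malignancy and occurring within 30 days of study product infusion". Item (b) is "Any treatment-emergent CTCAE Grade 3 CRS that do not resolve to" Grade 2 or lower within 7 days. The lead sentence also makes an attributable Grade III toxicity a DLT if it is one "that is not reversible within 4 weeks".

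The rules that use the DLT count are all set at 4 weeks:

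- Table 4 (9.1.1) is driven by the "Number of patients with DLT observed during the first 4 weeks after CAR treatment".
- The MTD (9.1.1) is the highest dose at which at most 1 of 6 patients "experiences DLT during the 4 week observation period after CAR treatment". Section 15.4 uses the same 4 weeks.
- The last patient in a cohort "should be observed for DLTs for at least 4 weeks prior to moving on to the next cohort/higher dose".
- A patient without a DLT is evaluable for the MTD if, among other things, they "have 4 weeks of follow-up for adverse events after the infusion" (9.4). Replacement (12.7.3) and the MTD Analysis Set (15.1) follow the same limit.

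Section 15.5 tabulates the proportion of patients with DLT at each dose level and gives no window.

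**The concern.** Two parts of the plan disagree about which events determine the primary endpoint. An organ toxicity on day 29 or 30 satisfies item (e) and is reportable to the FDA as part of the DLT definition, yet it lies outside Table 4 and the MTD count. The key secondary table in 15.5 could include it, so the primary and key secondary results could differ on the same patient. A patient lost to follow-up on day 29 is fully evaluable although the item (e) window is still open.

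The second gap is one of timing. Item (b) needs up to 7 days to classify a Grade 3 CRS. When onset is late in the window, those days run past the minimum hold, and the plan does not say whether to wait or how to count the patient.

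In a 3+3 design one event matters. A further DLT changes the action at 0 of 3, 1 of 3 and 1 of 6. For example, a level with 1 of 6 counted DLTs passes, although 2 of 6 patients may have a DLT by definition.

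**Working it through.** **Windows, taking infusion as day 0.** Four weeks is 4 × 7 = 28 days. Item (e) runs to day 30. The gap is 30 − 28 = 2 days, days 29 and 30.

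**Grade 3 CRS, with the 7 days taken from onset.**

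| Onset | Clock ends | Position at day 28 |
|---|---|---|
| Day 21 or earlier | 21 + 7 = day 28 or earlier | Classified |
| Day 22 | 22 + 7 = day 29 | Open |
| Day 28 | 28 + 7 = day 35 | Open |

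Only onset on days 22-28 is affected. A CRS that began by day 21 and is still Grade 3 at day 28 has already failed the 7-day test and is a DLT.

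**Effect of leaving out days 29-30.** The plan states no figure to reproduce here. Under Table 4 a level is cleared with 0 of 3 DLTs, or with 1 of 3 followed by 0 of 3:

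P(clear) = (1 − p)³ + 3p(1 − p)⁵

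Here p is the true 30-day DLT rate. The documents give neither a DLT rate nor an onset distribution, so both are assumed. If every DLT is an item (e) event and onset is uniform over 30 days, 2/30 = 6.7% fall on days 29-30 and the counted rate is q = p × 28/30.

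| p | q | P(clear), all counted | P(clear), 28 days | Difference (points) |
|---|---|---|---|---|
| 0.10 | 0.0933 | 0.9061 | 0.9169 | 1.1 |
| 0.20 | 0.1867 | 0.7086 | 0.7373 | 2.9 |
| 0.30 | 0.2800 | 0.4943 | 0.5358 | 4.2 |

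If half that share (3.3%) falls on days 29-30, the differences are 0.5, 1.4 and 2.1 points.

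Under uniform onset, the chance that at least one of three patients has a day 29-30 DLT is 1 − (1 − 2p/30)³, which is 2.0%, 4.0% and 5.9% at p = 0.10, 0.20 and 0.30.

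**Could the next dose be given before such an event is known?** After consent, patients have leukapheresis, about 6 weeks of RT with TMZ, up to three dose-intensified TMZ cycles, and at least 48 hours off TMZ (9.1). With no gaps, and no dose-intensified cycle counted, the lower bound from entry to infusion is 42 + 2 = 44 days. With three full cycles it is 42 + 28 + 28 + 21 + 2 = 121 days. The events in question are settled 2 days (day 30) or at most 7 days (day 35) after a 28-day hold ends.

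**The case against.** The strongest defence is that the MTD count is not ambiguous. Table 4, both MTD definitions and the MTD Analysis Set say 4 weeks, so a day 29 event is simply not counted. Nor is the event lost, because all AEs after infusion are recorded (section 13) and item (e) events go to the FDA. The 4-week observation period in 9.1.2 could also be read into 15.5. This stands as far as it goes: the data would exist, and the counting rule can be followed. It does not explain why the plan calls an event a DLT and then leaves it out of the DLT count.

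On CRS, the defence narrows the gap considerably. Worsening to Grade 4 or 5 counts at once under item (a). A Grade 3 CRS with a listed Grade 3 organ toxicity can count under item (e), which has no duration test. Section 9.1.3 describes severe reactions as rapid in onset. The hold is a minimum, so the team may wait. What remains is an isolated Grade 3 CRS first appearing in the fourth week, for which waiting is allowed but not required.

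Three stronger readings are tempting and are not supported:

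- **Any Grade 3 CRS still open at the end of the hold has no counting rule.** This fails for onset by day 21, as shown above.
- **Every lead-sentence Grade III event has the same gap.** That requires its 4 weeks to run from onset. The text does not say when they start. If they mean the observation period, an event still open at week 4 counts and there is no gap.
- **The next cohort would be dosed without knowledge of these events.** For patients entered after the hold, at least about 44 days pass before infusion.

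**Conclusion.** The plan is wrong as written on the window: a 30-day criterion sits inside a set of 4-week counting rules, and a day 29-30 organ DLT drops out of escalation and the MTD. The CRS gap is real but limited to onset on days 22-28. Both should be fixed because they touch the definition of the primary endpoint, and the correction is cheap.

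The numerical effect is probably small. The 1.1 to 4.2 point range rests wholly on assumed DLT rates, on every DLT being an item (e) event, and on uniform onset. If fewer events fall on days 29-30, the effect is smaller. The direct safety consequence is limited by the long interval between entry and infusion. The textual conflict depends on none of these assumptions.

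**What to change.** 1. Use one DLT window throughout. Thirty days is preferable, written into 9.1.1 (Table 4, the MTD definition and the hold), 9.1.2, 9.4, 12.7.3, 15.1, 15.4 and 15.5. This keeps the stricter safety definition. The cost is amendment wording and a hold two days longer. Changing item (e) to 4 weeks would also remove the conflict with a single edit, but it would narrow the safety definition.
2. Do not escalate while a Grade 3 CRS with onset in the window is still inside its 7-day resolution clock, and count it by its outcome. The cost is an occasional delay of up to 7 days. With a 30-day window, for example, onset on day 30 is settled by day 37.

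No separate restriction on restarting TMZ is needed. Section 9.1 places the clinic evaluation at about 28 days, and Table 6 (footnote 16) places the first 5-day cycle at about 1 month. The sample size does not change.
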